### 9.4 **SAFETY ANALYSES**

All safety measures will be analyzed using the ITT data set. For all statistical tests, an overall test will be done first to compare the safety measures among all groups

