#### 6.1.6 Surgery visit

Subjects that are found to have histologic evidence of disease on biopsies performed at Week 24 visit will undergo surgical excision. This visit should be scheduled to occur with 4 weeks of last dose of study drug and will be performed as standard of care treatment.

For lesions that display clinical partial response or stable disease and that show histologic evidence of disease on sampling biopsy at Week 24 visit, residual visible or palpable tumor of target lesion will be removed using the standard Slow Mohs micrographic surgery, margin-controlled excision with rush permanent sections. Two types of specimens will be surgically removed at the time of surgical excision. First, the area of known BCC will be excised and will include the pre-biopsy area. This specimen will be labeled the tumor “debulking” specimen.

Second, marginal tissue will be excised in an attempt to completely remove the tumor until clear surgical margins are obtained, providing the patient the known standard of care. This tissue will be labeled “tumor margins” specimen. Peripheral and deep margins will be examined and recorded if positive or negative. If either peripheral or deep margins is positive, additional surgical excisions will be done in the Mohs tissue orientation fashion until no tumor cells are observed and surgical margins are deemed negative, as is standard of care. In the event that only superficial BCC (sBCC) remains at the surgical margin, it will be at the discretion of the managing physician if further surgery, an alternative treatment modality, or observation will occur.

For lesions that were deemed by investigator to exhibit complete clinical response at week 24 visit, but were found to have residual disease on the sampling biopsy at week 24 visit, the debulking specimen will include area of known BCC as seen on histology.

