#### 6.1.8 **Observation period**

All subjects will be followed for the observation period of 1 year after discontinuation of study medication.

During the observation period the subjects will followed every 3 months for 1 year after last dose.

The following study procedures during observation period:

- Assessment of any changes (deletions, additions, or dose modifications) to medications.
- Complete physical examination including general appearance, skin exam, and visual inspection of target lesion(s) area.
- Vital signs (BP; heart or pulse rate; and oral, tympanic, or temporal temperature).
- Weight and height measurements.
- Urine pregnancy test ( $\alpha$ -hCG) only for women who are of childbearing potential for visits within 7 months of last dose of study drug.
- Photography and measurement of target lesion area
- Adverse Event (AE) Monitoring.
- Reminder to use effective measures to avoid pregnancy (for women who are of child bearing potential for visits within 7 months of last dose of study drug).
- PRO questionnaires will be performed by the subject (SKINDEX-16 and Functional Assessment of Cancer Therapy – General (FACT-G) at first visit during Observation period (3 months after discontinuing treatment).

If a subject is noted to have a recurrence of target lesion or new lesions suspicious for BCCs on any part of the body, biopsy will be performed to confirm diagnosis. If pathology is consistent with basal cell carcinoma, the subject will exit the Observation period and all treatment options

will be discussed with the subject. If Mohs micrographic surgery is determined to be the best therapeutic option, surgical excision and study procedures will be performed as described in Section 6.1.6.

Subjects who underwent surgical excision of the target lesion may elect to be followed by phone contact every 3 months to provide information on the status of the surgical site and occurrence of any adverse events.

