## **7. REPORTING OF ADVERSE EVENTS**

### **7.1 ASSESSMENT OF SAFETY**

Safety assessments will consist of monitoring and reporting adverse events (AEs) and serious adverse events (SAEs) that are considered related to study drug, all events of death, and any study specific issue of concern.

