#### **7.1.1 Adverse Events**

An AE is any unfavorable and unintended sign, symptom, or disease temporally associated with the use of an investigational medicinal product (IMP) or other protocol-imposed intervention, regardless of attribution.

This includes the following:

- AEs not previously observed in the subject that emerge during the protocol-specified AE reporting period, including signs or symptoms associated with Basal Cell Carcinoma that were not present prior to the AE reporting period.
- Complications that occur as a result of protocol-mandated interventions (e.g., invasive procedures such as cardiac catheterizations).

If applicable, AEs that occur prior to assignment of study treatment associated with medication washout, no treatment run-in, or other protocol-mandated intervention.

Preexisting medical conditions (other than the condition being studied) judged by the investigator to have worsened in severity or frequency or changed in character during the protocol-specified AE reporting period.

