### 7.2.1 **Adverse Event Reporting Period**

The study period during which all AEs and SAEs must be reported begins after informed consent is obtained and initiation of study treatment and ends 30 days following the last administration of study treatment or study discontinuation/termination, whichever is earlier. After this period, investigators should only report SAEs that are attributed to prior study treatment. Any subject who has an adverse event deemed related to the study treatment in this trial, will be followed until reversibility is established. This may occur after study completion at the subject's regular clinic follow-up visits.

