#### 9.4.1 **Adverse Events**

Adverse events will be summarized by using the NCI Common Terminology criteria for AE, version 4 (Appendix IX). The incidence of AEs (percent of subjects reporting the AE at least once). A separate tabulation of incidences will display only AEs coded as “probably” or “possibly” related to treatment.

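### The planned between-group safety test uses crude AE incidence, yet after the last dose both surgery and early AE contact depend on tumor clearance; surgery-type AEs can then differ between subtypes without any difference in drug harm.

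*Combined protocol and SAP*

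**What the plan says.** - **Test.** Section 9.4 analyzes safety on the ITT set and states that "an overall test will be done first to compare the safety measures among all groups". It names neither the groups nor the test.
- **Measure.** Section 9.4.1 uses incidence, defined as "percent of subjects reporting the AE at least once". A second table is limited to treatment-related AEs. Neither is restricted to time on drug.
- **AE window.** Section 7.2.1 says that the period for reporting all AEs "ends 30 days following the last administration of study treatment or study discontinuation/termination, whichever is earlier". After that, only SAEs attributed to treatment are reported.
- **AE definition.** Section 7.1.1 applies whatever the attribution and lists "Complications that occur as a result of protocol-mandated interventions". Section 7.1, by contrast, describes the safety assessments as covering AEs and "serious adverse events (SAEs) that are considered related to study drug", plus deaths and issues of concern.
- **Residual tumor at Week 24.** Section 6.1.6 sends these subjects to surgery: "This visit should be scheduled to occur with 4 weeks of last dose of study drug". An exit visit follows within 4 weeks of the operation (6.1.7) or 30 days after it (Appendix 6). Appendix 6 marks AE review at both visits.
- **Clearance.** These subjects enter observation. Section 6.1.8 says: "During the observation period the subjects will followed every 3 months for 1 year after last dose". Appendix 6 puts the first observation visit at Week 36, or at Week 24 for those who stopped at Week 12.

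**The concern.** While on drug, every subject is seen every 4 weeks and asked about AEs. Once the drug stops, what can happen to a subject, and when anyone asks about it, depends on whether the tumor cleared. The primary objective is to find out whether efficacy differs by subtype. If it does, the subtype groups will hold different proportions of operated subjects, and the test in 9.4 will partly compare surgery and visit timing rather than drug tolerability. This also affects subjects who complete all 24 weeks, so it is not just a consequence of the shorter exposure of those who stop at Week 12.

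**Working it through.** **1. Contacts after the last dose (day 0)**

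| | Residual tumor | Cleared |
|---|---|---|
| Operation | by day 28 | none |
| First AE contact | by day 28 | about day 84 |
| Second AE contact | by day 28 + 28 = 56 (6.1.7) or 28 + 30 = 58 (Appendix 6) | next 3-monthly visit |
| Scheduled contacts inside the 30-day window | at least 1 | 0 |

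A cleared subject with an event in the window reports it 84 − 30 = 54 to 84 days later, about 8 to 12 weeks. For a 24-week completer the window is 30/(168 + 30) = 15% of the AE period. That is a share of time, not of missed events.

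**2. Truncation of surgical events.** If surgery falls on day d, then 30 − d days of post-surgical follow-up lie inside the window. At d = 28 only 2 days remain.

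**3. What 9.1 does and does not supply.** The 9.1 intervals reproduce as p ± 1.96·√(p(1−p)/n):
- 12/16 gives 53.8%–96.2% (stated 54%–96%).
- 4/10 gives 9.6%–70.4% (stated 10%–70%).

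The first interval is described as being for a partial response rate, and the Appendix 6 schedule for partial response or stable disease leads to surgery. The 40% is merely the midpoint of the second interval. Neither figure is the share entering observation. The only complete-response figure in the documents is 2 of 33 (6%), from the Phase I trial in advanced disease (Section 1.3).

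**4. Illustrative size.** Let c be the proportion cleared and s the proportion of operated subjects with a surgery-type AE counted in the window. Incidence of that AE is (1 − c)·s, so the gap between two groups is s·(c₁ − c₂). All values of c and s below are assumptions. Giving the nodular group the higher clearance is also an assumption. Rejection is the exact probability that a three-group Pearson chi-square at 0.05 (n = 16/10/10) is significant when drug toxicity is equal. Section 9.4 names no test, and the 0.05 is stated only in 9.3.3.1.1.

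| Clearance, nodular / each other group | s | Incidence | Gap (points) | Rejection |
|---|---|---|---|---|
| 75% / 40% | 10% | 2.5% vs 6% | 3.5 | 1.6% |
| | 30% | 7.5% vs 18% | 10.5 | 9.5% |
| | 50% | 12.5% vs 30% | 17.5 | 19.8% |
| 75% / 20% | 10% | 2.5% vs 8% | 5.5 | 2.9% |
| | 30% | 7.5% vs 24% | 16.5 | 18.7% |
| | 50% | 12.5% vs 40% | 27.5 | 38.9% |
| 50% / 20% | 10% | 5% vs 8% | 3.0 | 2.1% |
| | 30% | 15% vs 24% | 9.0 | 9.0% |
| | 50% | 25% vs 40% | 15.0 | 13.3% |
| 6% / 0% | 20% | 18.8% vs 20% | 1.2 | not run |
| | 50% | 47% vs 50% | 3.0 | not run |

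**5. Any AE.** With background AE risk b, equal in all groups, the gap shrinks to (1 − b)·s·(c₁ − c₂). At an assumed b = 90%, the largest case is 0.10 × 0.50 × 0.55 = 2.8 points. Rejection is then 1%–2%, no higher than the 2.2% found when the groups are truly equal.

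**The case against.** The case for leaving the plan alone has several parts.

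- **Large numbers are tempting but unsupported.** A reader might take 75% and 40% from 9.1 as the shares entering observation and infer a bias of 7 to 17.5 points at surgical AE rates of 20%–50%. The documents do not support this, because those figures concern response, not clearance. With 6% against 0% cleared, the same surgical rates give 1.2 to 3 points. A reader might also compute 30/114 = 26% of the AE period for Week 12 stoppers. That figure has no surgical comparator, since no Week 12 path leads to scheduled surgery (6.1.3). Both parts of this objection stand.
- **Surgical events may be few in the data.** The operation can fall near the end of the window, and the exit visit can fall outside it. This stands, and it lowers s.
- **Surgery is called standard of care, so its complications may not be AEs here.** This stands only in part. The definition in 7.1.1 also covers any unfavorable event temporally associated with the drug, whatever its cause. Section 7.1 can be read more narrowly, so the scope is unsettled.
- **The related-only table drops surgical events.** It does, but it is an additional tabulation, and 9.4 does not make it the tested measure. It also uses probable/possible codes, whereas 7.2.2 records causality as yes or no.
- **Cleared subjects are monitored.** True: they have four observation visits with AE review. The difference is timing and recall, not absence of follow-up.
- **Section 6.6.2 requires Mohs excision after any study medication.** Taken literally, this would remove the surgical contrast. It conflicts with 6.1.4, 6.1.6 and the observation schedules in Appendix 6.

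**Conclusion.** The concern holds in a limited form. The operation and the timing of AE contact after the last dose depend on clearance, and the planned incidence test does not separate those events. A spurious between-group difference follows only if clearance differs by subtype and surgical or early post-dose events are recorded as AEs. Reading 9.4 as a comparison of subtype groups is an inference, though no other groups are defined.

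The effect is mainly on surgery-type AEs: about 1 to 28 points across the assumed rates, with no basis in the documents for choosing a value. For any-AE incidence at a 90% background it is under 3 points. A reader might infer that the better-responding subtype will look safer overall. The documents do not support that: it depends on a clearance difference not yet known, and it is negligible for common events. The half-length exposure of Week 12 stoppers is a separate matter that pushes crude incidence the same way.

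This is a modest defect in a 36-subject pilot, worth correcting because the correction is cheap.

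**What to change.** In Section 9.4:

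1. Name the groups and the test.
2. Base the between-group comparison on events with onset from first dose to the last-dose visit, excluding events attributed to surgery.
3. Because Week 12 stoppers have 12 rather than 24 weeks on drug, either adjust for exposure or restrict the comparison to the first 12 weeks, which all planned paths share. Exposure adjustment keeps later events but, as a simple rate, assumes a roughly constant hazard. The 12-week window avoids that assumption but ignores later on-drug events.
4. Tabulate events with onset after the last dose separately by path (surgery or observation), with surgical complications on their own line.

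Two sets of sections must also be reconciled: 6.6.2 with 6.1.4 and 6.1.6 on who has surgery, and 7.1 with 7.1.1 and 7.2 to 7.2.2 on which AEs are collected.

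The cost is SAP wording and one extra table, with no new data. The downside is that drug events first appearing after the last dose leave the group test, though they are still reported.

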#### 9.4.1 **Adverse Events**

Adverse events will be summarized by using the NCI Common Terminology criteria for AE, version 4 (Appendix IX). The incidence of AEs (percent of subjects reporting the AE at least once). A separate tabulation of incidences will display only AEs coded as “probably” or “possibly” related to treatment.

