### 2.2 SECONDARY OBJECTIVES

- To evaluate the onset of efficacy of vismodegib during 24 weeks of treatment in various histologic subtypes of high risk and/or locally advanced basal cell skin cancer
- To evaluate the safety and tolerability of vismodegib over 24 weeks of treatment in subjects with high risk and/or locally advanced basal cell skin cancer
- To evaluate patient reported outcome (PRO) measures during 24 weeks of treatment with vismodegib in subjects with high risk and/or locally advanced basal cell skin cancer

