## 3. STUDY DESIGN

This is a Phase 2B two-site, open-label, nonrandomized 24-week study of the efficacy and safety of vismodegib (150 mg PO daily) in subjects with high risk and/or locally advanced basal cell carcinoma. A total of 36 subjects with infiltrative/morpheaform, nodular, or superficial BCC will be enrolled in the study. Each subtype group will have a minimum of 10 subjects. No group will have more than 16 subjects.

At Treatment Initiation Visit (Baseline/Day 1), eligible subjects will begin a 24-week treatment regimen with vismodegib 150 mg daily. Clinical assessments will be performed every 4 weeks during treatment. Intra-treatment tissue histopathologic evaluation will be conducted at Week 12. Subjects will be eligible to discontinue treatment early and enter the Observation period if there is no histologic evidence of tumor on Week 12 pathology specimens. Post-treatment histopathologic evaluation will be performed at Week 24 (End of Treatment visit). Subjects will be eligible to enter the Observation period in lieu of surgery if their target lesion displays complete histologic response on biopsy specimens obtained at Week 24 visit. For subjects with histologic evidence of disease on pathology at Week 24 visit, surgical excision or Mohs surgery on the target lesion will be performed within 4 weeks of the last dose of study drug. Patient Reported Outcomes (PRO) data will be collected at baseline visit, during treatment, end of treatment/early termination visit, surgical visit, and study exit (post-surgery) visit, and at first Observation period visit (when applicable) Safety assessments including adverse event (AE) monitoring and concomitant medications will be performed at each visit.

The rationale for using 24-week treatment schedule was based on previous data from pilot studies. Data from a previous trial of 33 subjects with advanced BCC, demonstrated that 94% (17/18) of responders responded by 24-weeks. (Von Hoff et al 2009) In non-responders, treatment beyond 24 weeks may unnecessarily endanger the patient and allow their basal cell skin cancer to progress potentially negatively affecting clinical outcome.

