At week 12, Intra-treatment tissue histopathologic evaluation will be performed to assess histologic response. For subjects with apparent clinical complete response at Week 12 and no histologic evidence of disease is observed, subjects will enter the observation period and be followed clinically every 3 months up to one year (See Appendix 5, Figure 3 for more

information). Sample diagrams demonstrating the sites of screening biopsies and Week 12 biopsies for a tumor is seen in Section 6.1.3.

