### 6.1.3 Intra-treatment Tissue Histopathologic Evaluation

All subjects will undergo intra-treatment Tissue Histopathologic Evaluation at Week 12 visit. For lesions that display complete clinical response, histologic presence or absence of tumor on biopsy determines whether or not the subject is eligible to end treatment early and enter the Observation period (See Appendix 5 , Figure 3). Subjects with clinical partial response or stable disease at Week 12 visit will continue treatment for the full duration of 24 week regardless of pathology on sampling biopsy (See Appendix 5, Figure 2).

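### Adverse event incidence is planned only as a crude percentage of subjects, although clearance at Week 12 ends dosing early, so 24-week on-drug risk is understated if some first events would start later

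*Combined protocol and SAP*

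**What the plan says.** Section 2.2 sets the safety objective: "To evaluate the safety and tolerability of vismodegib over 24 weeks of treatment". Section 9.4.1 gives the measure: "The incidence of AEs (percent of subjects reporting the AE at least once". Section 9.4 gives the analysis set, "All safety measures will be analyzed using the ITT data set", and adds that "an overall test will be done first to compare the safety measures among all groups". It does not name the test or define the groups.

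Time on drug depends on response. Section 6.1.2 (Interval Visits) says: "For subjects with apparent clinical complete response at Week 12 and no histologic evidence of disease is observed, subjects will enter the observation period". Section 6.1.3 says that, for lesions in complete clinical response, "histologic presence or absence of tumor on biopsy determines whether or not the subject is eligible to end treatment early". It also says: "Subjects with clinical partial response or stable disease at Week 12 visit will continue treatment for the full duration of 24 week". Section 3 is worded differently: "Subjects will be eligible to discontinue treatment early and enter the Observation period if there is no histologic evidence of tumor". There the Week 12 stop is an option and no clinical response is mentioned. In Appendix 6, the schedule for Week 12 complete responders shows no study drug after that visit.

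Section 7.2.1 closes general adverse event reporting 30 days after last dose or at study discontinuation, whichever is earlier. Section 6.1.8 and Appendix 6 nevertheless list adverse event monitoring at the observation visits. Section 9.4.1 does not say which events count.

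Two other items touch on time. Section 9.3.2.2 names onset of specific adverse effects as an endpoint, but no onset analysis follows in 9.3.3.2.2 or 9.4. Section 9.3.3.2.2 reports the percentage completing 24 weeks, and mean and median treatment time for those unable to complete. Neither is linked to adverse event incidence.

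**The concern.** A crude percentage estimates risk over 24 weeks on drug only if nearly everyone is on drug for 24 weeks. Here the subjects who do best stop at half that time by design. They stay in the denominator but have half the opportunity to contribute an on-drug event. Under the Section 7.2.1 window their general reporting ends near Week 16.3 (12 + 30/7), against Week 28.3 for completers.

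Two things are at stake. The figure reported against the Section 2.2 objective may be too low. In addition, response by subtype is the trial's primary question, so Week 12 stop shares may well differ between subtypes. Reported event rates could then differ between subtypes whose true risk on drug is the same.

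**Working it through.** The documents give no adverse event rate, no Week 12 clearance rate and no safety power, so there is no plan figure to reproduce for this point. The values below are assumptions.

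**Inputs**
- R, true risk of a first event over 24 weeks on drug: assumed 60%, range 30% to 80%.
- f, share stopping at Week 12 for clearance: assumed 6% to 50%. The low end matches the only complete-response figure in the documents, 2/33 = 6% in the earlier Phase I trial (Section 1.3). That trial was in advanced or metastatic disease, so the figure is only indicative.
- Timing of first events: constant hazard, then front-loaded.
- Group sizes 10, 16 and 10: the split used in Section 9.1.

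**Crude percentage against 24-week risk**
- Hazard h = −ln(1 − 0.60)/24 = 0.0382 per week.
- 12-week risk r12 = 1 − exp(−12h) = 1 − √0.40 = 0.368.
- Expected crude percentage = (1 − f) × R + f × r12.

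| f | Crude percentage | Shortfall from 60% |
|---|---|---|
| 6% | 58.6% | 1.4 points |
| 15% | 56.5% | 3.5 points |
| 30% | 53.0% | 7.0 points |
| 50% | 48.4% | 11.6 points |

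Over f = 6% to 50%, the shortfall is 0.8 to 6.8 points for R = 30% (r12 = 0.163) and 1.5 to 12.4 points for R = 80% (r12 = 0.553).

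**Front-loaded events.** If a share q of first events occurs by Week 12, the shortfall is f × R × (1 − q). With R = 60% and q = 0.9 it is 0.4 to 3.0 points for f = 6% to 50%. With q = 1 it is zero.

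**Time-based estimates.** In simulation at f = 15%, 30% and 50%, with time at risk ending at last dose and a constant hazard, the Kaplan-Meier estimate at Week 24 and the exposure-adjusted rate (converted to a 24-week risk) both return 60%.

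**Where to censor.** Suppose time at risk ran to 30 days after last dose and the off-drug hazard were zero. With f = 30%, Week 24 survival is exp(−12h) × [0.7 × exp(−4.29h) + 0.3] × exp(−7.71h) = 0.632 × 0.894 × 0.745 = 0.421. The estimate is then about 58% rather than 60%, because cleared subjects are counted as at risk while off drug.

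**Between subtypes.** Take R = 60% in every subtype and Week 12 stop shares of 10%, 20% and 50% (infiltrative/morpheaform, nodular, superficial). Expected crude rates are 57.7%, 55.4% and 48.4%, a gap of about 9 points with no true difference. In 100,000 simulated trials, a three-group Pearson chi-square test at 0.05 rejects in 6.1%, against 4.8% with no early stopping. Over the other constant-hazard settings tried, rejection runs from 5.1% to 9.8%. The top value needs R = 80% and stop shares of 0%, 20% and 60%. With 90% of events by Week 12 and R = 60%, rejection stays below 5%.

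**The direction can reverse.** Suppose 10% of a poorly responding group stop at Week 12 for clearance and 20% stop at Week 8 for progression. The 8-week risk is 1 − exp(−8h) = 0.263. The crude rate is 0.7 × 0.60 + 0.1 × 0.368 + 0.2 × 0.263 = 50.9%. That is below the 53.0% of a group in which 30% stop at Week 12 for response.

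**The case against.** The best defence is that the crude percentage is a valid answer to a different question: how many subjects have an event under the response-guided schedule as delivered. This stands, and is the reason to keep it. It does not answer Section 2.2, which speaks of 24 weeks of treatment.

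The bias may also be small. By Sections 6.1.2 and 6.1.3 the early stop needs both clinical and histologic clearance. At f = 6% the shortfall is 1.4 points, about half a subject in 36 (0.014 × 36 = 0.5), against a 95% half-width of 16 points around 60% (1.96 × √(0.24/36)). If events come early it is smaller still. This stands too: the size is unknown, and only the direction is known, provided some first events would begin on drug after Week 12.

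A reader might infer that the plan makes better-responding subtypes look safer, or that the overall safety test is seriously invalid. The documents support neither. Stopping for progression (Section 6.6.1) or for adverse events (Section 6.6.2) also shortens exposure and can offset or reverse the pattern. The test is moved little in most settings tried. Section 9.4 does not define its groups; histologic subtype is the natural reading in a single-regimen study, but it is a reading.

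Nor is time wholly ignored, since treatment time is summarised for non-completers. But that summary does not clearly cover subjects who stop by design, and it does not adjust any event rate.

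**Conclusion.** The point holds in limited form. Exposure depends on response, the measure ignores exposure, and nothing else planned corrects for it. The crude percentage therefore lies below 24-week on-drug risk if some first events would have started after Week 12. With R = 60% and a constant hazard the shortfall is about 1 to 12 points for stop shares of 6% to 50%. It is 0.4 to 3.0 points if 90% of first events occur by Week 12, and nil if all do. The risk, the stop share and the timing are all assumptions.

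Reported rates can differ between subtypes of equal true risk when their early-stop shares differ, by about 9 points in the example. The direction of that difference is not assured, and the effect on the overall test is generally small with 10 to 16 subjects per group. The main worry is how the reported percentages will be read, more than false rejection. The unsettled counting window adds to it: counting events at observation visits would mix off-drug time into the same percentage.

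**What to change.** Amend Sections 9.3.3.2.2, 9.4 and 9.4.1 as follows:

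1. Keep the crude counts and percentages, labelled as risk under the schedule as delivered.
2. State one adverse event counting window, reconciling Section 7.2.1 with Section 6.1.8 and Appendix 6. The Week 12 stopping wording in Sections 3, 6.1.2 and 6.1.3 should also be reconciled, because it determines who has short exposure.
3. Report treatment duration by subtype for all subjects, not only those unable to complete.
4. For all subjects together, add on-treatment exposure-adjusted event rates and cumulative incidence of first event to Week 24, with 95% intervals. End time at risk at last dose, and give a version with 30 days added as a sensitivity analysis. State the assumption that adverse event risk is unrelated to response.
5. Define the groups in Section 9.4, and make any subtype comparison over the common first 12 weeks, before response-based stopping.

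The data are already collected: event start dates (Section 7.2.2) and dosing diaries (Section 6.1.2, Interval Visits). The cost is a little more analysis. The downside is that the Week 24 estimate rests on the censoring assumption in item 4: if subjects who clear early have a different adverse event risk, it is biased.
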